### Data Included

Same as the main estimator.

### Missing Data Handling Rule

Same as the main estimator.

## Analysis Methods

Cochran-Mantel-Haenszel test stratified by the type of MAC (*M. avium* only or other) at the 5% 2-sided significance level will be used to compare sputum culture conversion rate in MGIT at Week 24. The proportion of the participants with sputum culture conversion at Week 24 will be summarized as randomized and the stratum adjusted treatment difference with 2-sided 95% CI will also be presented.

### 5.3.3. Supplementary Estimand

The supplementary estimand is defined with considering treatment regimen change under treatment policy strategy.

- Population: Adult patients with treatment-refractory MAC-LD
- Endpoint: Proportion of participants with sputum culture conversion in MGIT at Week 24.
- Treatment: BDQ-containing regimen versus rifamycin-containing regimen.
- Population Level Summary: The difference of proportions between treatment groups.
- Intercurrent Events (ICE):
  - a. Deaths and treatment discontinuation will be handled by a composite strategy to treat the participants as nonconverters.
  - b. Treatment regimen change prior to Week 24: if the participant change treatment regimen prior to Week 24 but microbiology assessments are available at that time point, all data will be used regardless of occurrence of the intercurrent event (treatment policy strategy).

Major protocol deviations (besides treatment discontinuation prior to Week 24): all data will be used regardless of the occurrence of major protocol deviations (treatment policy strategy).

#### 5.3.3.1. Main Estimator of the Supplementary Estimand

##### Assumptions

Same as for the main estimator of the primary estimand.

##### Data Included

All randomized participants who take at least 1 dose of study intervention will be used.

##### Missing Data Handling Rule

Same as for the main estimator of the primary estimand.

## Analysis Methods

The Cochran-Mantel-Haenszel test stratified by region (at the 5% 2-sided significance level) will be used to compare sputum culture conversion rate in MGIT at Week 24. The proportion of the subjects with sputum culture conversion at Week 24 will be summarized as randomized and the treatment difference with 2-sided 95% CI will also be presented.

### **5.3.4. Subgroup Analyses of Primary Efficacy Endpoint**

All categorical variables described in Section 6.3 will be used for subgroup analysis, and the treatment difference of proportion of the subjects with sputum culture conversion will be presented with 95% CI. The subgroup analysis will be applied for the primary estimand.

## **5.4. Secondary Endpoints Analysis**

### **5.4.1. Key Confirmatory Secondary Endpoints**

No key confirmatory secondary endpoints are defined in this study.

#### **5.4.1.1. Definition of Endpoints**

Not applicable.

#### **5.4.1.2. Estimands**

Not applicable.

#### **5.4.1.3. Analysis Methods**

Not applicable.

### **5.4.2. Supportive Secondary Endpoints**

#### **5.4.2.1. Definition of Endpoints**

##### **Sputum culture conversion in MGIT and 7H10 or 7H11 agar media**

The definition of sputum culture conversion is described in Section 5.3.1.

##### **Sputum culture negativity in MGIT and 7H10 or 7H11 agar media**

The percentage of participants with sputum culture negativity in MGIT and 7H10 or 7H11 agar media will be calculated at each visit after Week 2, respectively. No imputation rules will be applied for withdrawn and missing data.

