### 6.8.2. Optional Cohort

To maximize the benefit and minimize the risk, participants in treatment Group B can switch to optional cohort after completion of Week 24 assessment. The decision to switch to optional cohort can be made by Week 32 (refer to Sections 1.2, 1.3 and 4.1). Participants must meet all of the following criteria at the timing of the decision to switch to optional cohort. Before starting BDQ administration, a washout of rifamycin for 2 weeks is required and BDQ administration in optional cohort should start by OPD1.

- Participants are non-converter based on the result of microbiological test (ie, positive) up to Week 24.
- Participants do not have condition described in Section 7.1.
- Participants do not experience any AE associated with CAM and/or EB that causes discontinuation of CAM and/or EB at the discretion of investigators.

Switching from an individualized treatment regimen to the optional cohort is not permitted.

Switching to an individualized treatment regimen is permitted if the criteria described in Section 6.8.1 are met, even after switching to the optional cohort.

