## 3. SAMPLE SIZE DETERMINATION

Based on the results of 2 clinical studies in AMK liposome inhalation suspension (ALIS, Arikayce®), (Phase 2 [[Griffith 2018](#)] and Phase 3 [[Olivier 2017](#)]) in an analogous population, it is

anticipated that the rifamycin-containing regimen in this study will have a sputum culture conversion rate assumed to be equal to 10% after 24 weeks of treatment.

A sample size of 124 participants (62 in Group A: the BDQ containing regimen, 62 in Group B: the rifamycin-containing regimen) will have a power of about 80% to show superiority for a 20% difference in proportion of participants having sputum conversion at Week 24 based on a chi-square test (at the 5% 2-sided significance level) on the intent-to-treat (ITT) population.

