#### **5.3.2. Primary Estimand**

The main clinical quantity of interest to be estimated in this study, is defined by the following 5 components:

- Population: Adult patients with treatment-refractory MAC-LD
- Endpoint: Proportion of participants with sputum culture conversion (sputum culture conversion rate) in MGIT at Week 24.
- Treatment: BDQ-containing regimen versus rifamycin-containing regimen.
- Population Level Summary: The difference of proportions between treatment groups.
- Intercurrent Events (ICE):
  - a. Deaths, treatment discontinuation and treatment regimen changes prior to Week 24: all these ICEs will be handled by a composite strategy to treat the participants as nonconverters.
  - b. Major protocol deviations (besides treatment regimen changes prior to Week 24): all data will be used regardless of the occurrence of major protocol deviations (treatment policy strategy).

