### 5.4.2.2.3. Sputum culture negativity in MGIT and 7H10 or 7H11 agar media

The percentage of participants with sputum culture negativity in MGIT and 7H10 or 7H11 agar media will be also summarized at each visit after Week 2, respectively. After Week 24, the percentage of participants with sputum culture conversion in optional cohort will be also summarized.

Sputum culture negativity in MGIT at Week 24: The Cochran-Mantel-Haenszel test stratified by region (at the 5% 2-sided significance level) will be used to compare sputum culture negativity in MGIT at Week 24. The proportion of the subjects with sputum culture negativity at Week 24 will be summarized as randomized and the treatment difference with 2-sided 95% CI will also be presented. A generalized linear model including treatment, region (Japan, non-Japan), time, and treatment-by-time interaction terms will be applied for the number of negative participants and the number of all participants at each timepoint and comparison between treatment groups will be performed using the appropriate contrast for the percentage of negative participants at Week 24. If the subjects switch to individualized treatment regimen or to optional cohort, sputum culture should be considered as not negative.

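### The Week 24 culture-negativity comparison counts regimen switchers as not negative but has no matching rule for participants who die, stop treatment or leave the study

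*SAP*

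**What the plan says.** SAP 5.4.2.1, under sputum culture negativity, defines a percentage at each visit after Week 2 and states: "No imputation rules will be applied for withdrawn and missing data".

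SAP 5.4.2.2.3 adds a rule for one kind of failure: "If the subjects switch to individualized treatment regimen or to optional cohort, sputum culture should be considered as not negative". The same section plans two Week 24 comparisons. A CMH test stratified by region, at the two-sided 5% level, "will be used to compare sputum culture negativity in MGIT at Week 24". A generalized linear model, with a contrast at Week 24, "will be applied for the number of negative participants and the number of all participants at each timepoint".

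For the primary endpoint, SAP 5.3.2 lists death, treatment discontinuation and regimen change before Week 24 together and says that "all these ICEs will be handled by a composite strategy to treat the participants as nonconverters".

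On the status of the endpoint, SAP 5.4.1 says: "No key confirmatory secondary endpoints are defined in this study". Culture negativity is among the supportive secondary endpoints in SAP 5.4.2.

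**The concern.** Three kinds of failure that the primary estimand treats alike are handled differently here. A participant who switches to an individualized regimen stays in the denominator as not negative. One who dies or leaves the study has no Week 24 culture and, with no imputation, is most naturally left out. One who stops treatment but stays and produces a negative culture is caught by no rule in SAP 5.4.2.2.3 and can count as negative.

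Which route a participant takes depends partly on which drug fails. All the individualized regimens in Protocol 6.8.1 retain the study intervention and clarithromycin. A participant who has to stop ethambutol can therefore become a switcher, whereas one who has to stop bedaquiline, rifamycin or clarithromycin is directed out of the study. Protocol 7.2, however, says that stopping study intervention does not by itself mean withdrawal, so some who stop may continue to give sputum. The reasons for leaving may differ by arm in an open-label trial: QT prolongation is a listed risk of bedaquiline and clarithromycin, and conversion on the control regimen is expected to be low.

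At stake is a Week 24 comparison, tested at 5%, that could differ from the primary result only because of who is counted.

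**Working it through.** **Inputs from the documents.** 62 participants per arm, a two-sided 5% test, and planning rates of 10% v 30% (SAP 3). Those rates are for conversion; no negativity rate is given. No loss rate is given for either arm.

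**Assumptions.** A composite rate (losses counted as not negative) of 10% to 30%, and loss before Week 24 of 0% to 30% per arm.

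**The plan's own figure.** Power = Φ[(Δ√n − 1.96√(2p̄(1−p̄))) / √(p₁(1−p₁) + p₂(1−p₂))]. With n = 62, Δ = 0.20 and p̄ = 0.20, this is Φ[(1.575 − 1.109)/0.548] = Φ(0.851) = 0.803. The stated power of about 80% is reproduced for the primary endpoint.

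**Effect of leaving losses out.** If those lost would have counted as not negative, observed-case rate = composite rate / (1 − loss). For example, 0.30/0.80 = 0.375 and 0.30/0.95 = 0.316. In participants, 0.30 × 62 = 18.6 negatives are divided by 49.6 in one arm and 58.9 in the other.

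The table takes a composite rate of 30% in **both** arms. Rejection rates come from 400,000 simulated trials per row, using an unstratified pooled z-test in place of CMH.

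| Assumed loss | Observed-case rates | Apparent difference (points) | Null rejection |
|---|---|---|---|
| 10% v 10% | 33.3% v 33.3% | 0 | 5.1% |
| 20% v 20% | 37.5% v 37.5% | 0 | 5.1% |
| 10% v 5% | 33.3% v 31.6% | 1.8 | 5.6% |
| 20% v 5% | 37.5% v 31.6% | 5.9 | 10.1% |
| 30% v 5% | 42.9% v 31.6% | 11.3 | 21.9% |

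In the 20% v 5% row, 9.6 of the 10.1 percentage points favour the arm with more losses. Lower composite rates weaken the effect: at 20% v 5% loss, rejection is about 8.0% for a composite rate of 20% and about 6.4% for 10%. With every loss kept in the denominator as not negative, null rejection is 4.7% to 5.1% throughout.

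**With a real difference.** Take composite rates of 30% v 10%. Losses of 20% in Group A and 5% in Group B show as 0.375 − 0.105 = 27.0 points, with rejection of 92.8%. The reverse losses show as 0.316 − 0.125 = 19.1 points, with rejection of 67.6%. The composite denominator gives 20 points and 81% either way.

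**Losses unrelated to culture status.** Observed-case rejection under the null stays at 4.9% to 5.1% even at 30% v 5% loss. Counting the same losses as not negative then gives 7.9% to 16.0%, almost all against the arm with more losses.

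**The case against.** The strongest reply is that the SAP nowhere says that withdrawn participants leave the denominator. The model is fitted to negatives out of all participants at each timepoint, which could mean the whole ITT set. A reader might infer that a complete-case denominator is written into the plan; it is not. What stands against the reply is that keeping a participant without a culture in the denominator already treats them as not negative, which is an imputation, and SAP 5.4.2.1 rules imputation out. If the model wording does mean all ITT, the two sections disagree and two programmers could produce different Week 24 results.

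Second, a reader might infer that the rate is always inflated in whichever arm loses more participants. That does not follow. The losses must be unequal and the lost participants must be less often negative, or the composite must be taken as the target. Neither approach is neutral: the composite penalises the arm with more losses when the losses have nothing to do with culture status.

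Third, many failures are already captured. Non-response with clinical worsening and regimen-related adverse events can both lead to an individualized regimen, and those participants count as not negative. Optional-cohort switching plays no part at Week 24, because "participants in treatment Group B can switch to optional cohort after completion of Week 24 assessment". Only individualized-regimen switchers create the contrast with withdrawals at that visit. This narrows the problem but does not remove it, since participants who have to stop the study intervention or clarithromycin have no such regimen open to them.

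Fourth, the endpoint is supportive. That point stands in full.

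**Conclusion.** The concern holds as a conditional one. As written, the rules handle switching and other treatment failure differently, unlike the sponsor's own composite strategy for the primary endpoint, and the Week 24 negativity rate **can** favour the arm with more losses. The size cannot be fixed from the documents. Under the assumed 30% composite rate it runs from nothing with equal losses, through 1.8 points at 10% v 5%, to 5.9 points and about 10% null rejection at 20% v 5%. These figures rest on an observed-case denominator and on losses that are all failures.

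A reader might also infer that the primary result is at risk. It is not: the primary analysis already counts death, discontinuation and regimen change as nonconversion, and no confirmatory claim rests on negativity. The change is worth making because it is cheap and gives the two endpoints consistent rules, not because the trial's conclusion depends on it.

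**What to change.** In SAP 5.4.2.1 and 5.4.2.2.3, for the Week 24 comparison and the by-visit rates:

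- Count ITT participants who died, discontinued treatment or left the study before the visit as not negative, and keep them in the denominator, as for switchers and as in the primary estimand.
- Exclude from a visit's denominator only participants still on assigned treatment whose culture at that visit is intermittently missing or contaminated.
- Use this one denominator in both the CMH test and the generalized linear model.
- Keep the observed-case analysis as a sensitivity table.

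The cost is about two SAP sentences and one reprogrammed derived variable. The downside is that reported negativity rates fall (in the example, from 37.5% to 30% in the arm with 20% loss), and the arm with more losses is penalised if those losses are unrelated to culture status. The sensitivity table would let a reader see how much the result depends on that choice.

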##### **Time to sputum culture conversion in MGIT**

For this time-to-event analysis, an event is defined as sputum culture conversion in MGIT. The definition of sputum culture conversion is described in Section 5.3.1.

The date of event is defined as the date of the first of 3 consecutive negative sputum cultures taken at least 25 days apart. For subjects who achieve culture conversion after switching to individualized treatment regimen, the culture conversion after switching will not be treated as an event.

The rules of censoring are as follows.

Analysis period	Rules of censoring
From Day 1 to Week 24	
 
● If study discontinuation before event, date of censoring will be study discontinuation date.
 
● If no study discontinuation and no event, date of censoring will be the last sputum culture test date.
 

From Day 1 to Week 48	
 
● If switching to optional cohort before event, date of censoring will be the last sputum culture test date before switching to optional cohort.
 
● If study discontinuation before event, date of censoring will be study discontinuation date.
 
● If no switching to optional cohort and no study discontinuation and no event, date of censoring will be the last sputum culture test date.
 

From Optional Day 1 to Optional Week 48 (only for subjects who switched to Optional Cohort)	
 
● If study discontinuation before event, date of censoring will be study discontinuation date.
 
● If no study discontinuation and no event, date of censoring will be the last sputum culture test date.
 

### **Time to positivity in MGIT**

Time to positivity is calculated as the time required to positive signal in MGIT. If the qualitative result is “Negative”, time to positive signal is set to 42 (days). No imputation rules will be applied for withdrawn and missing data. If there are multiple positive samples, mean value will be used.

### **St. George’s Respiratory Questionnaire (SGRQ)**

The SGRQ responses are used to assess the subjects’ quality of life by evaluating 3 health domains: symptoms (Part1), and activity and impacts (both Part 2). Higher domain scores indicate more limitations. The composite total score is derived from the 3 domain scores. Each domain score and the total score has a range of 0 to 100, with 0 indicating the best possible quality of life. For treatment comparison at Week 24, if a part of score is missing at Week 24, the imputation rule will be applied based on SGRQ manual (VTMF-10523342).

### **Lung function parameters**

The lung function parameters including forced expiratory volume in one second, forced vital capacity, inspiratory capacity, functional residual capacity, and total lung capacity, will be assessed.

## 5.4.2.2. Analysis Methods

### 5.4.2.2.1. Sputum Culture Conversion in 7H10 or 7H11 Agar Media

Sputum culture conversion at Week 24: The Cochran-Mantel-Haenszel test stratified by region (at the 5% 2-sided significance level) will be used to compare sputum culture conversion rate in MGIT at Week 24. The proportion of the subjects with sputum culture conversion at Week 24 will be summarized as randomized and the treatment difference with 2-sided 95% CI will also be presented. The definition of sputum culture conversion is described in Section 5.3.1.

Sputum culture conversion at Week 48 and Week 60: The proportion of participants who achieved sputum culture conversion of each treatment group (ie, as randomized) will be calculated with 95% CI. Participants requiring a treatment regimen change to individualized regimen will also be considered as nonconverters.

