Upon completion of the 48-week treatment period, the participants in Group A who achieved culture conversion will transfer to the follow-up period of 12 weeks. During the follow-up period, the converters will be treatment free for MAC-LD in order to confirm the durability of culture conversion. Non-converters at Week 48 in Group A will be discontinued from the study and switched to another treatment regimen if they continue chemotherapy because the duration of BDQ treatment is 48 weeks. On the other hand, the participants in Group B will continue the study intervention up to Week 60. Upon completion of the 60-week study intervention period, the study is completed, but the participant may continue SOC of local guidelines or medical practice at each study site for at least 1 year after culture conversion at the discretion of the investigators.

In addition, this study provides an option to receive BDQ-containing regimen (BDQ + CAM + EB) for non-converters in Group B at Week 24 as the optional cohort. The participants may continue Group B regimen, switch to an individualized treatment regimen, or BDQ-containing regimen in the optional cohort at the discretion of the investigators. The criteria for switching to optional cohort after Week 24 are detailed in Section 6.8.2. When the investigator changes to BDQ-containing regimen, 2-week washout of rifamycin is required before initiation of BDQ-containing regimen. The participants switching to BDQ-containing regimen will be considered treatment failures for rifamycin-containing regimen and will be followed up for efficacy and safety for BDQ-containing regimen.

In this optional cohort, during the 48-week treatment period (from Day 1 in optional cohort [OPD1] to Week 48 in optional cohort [OPW48]) of the study, participants may be changed to individualized treatment regimen. The investigators can postpone the decision to transfer to the optional cohort for up to Week 32 in order to confirm a sputum culture positive at Week 24, if necessary. Regardless of delay in the transition phase, the treatment duration of the optional cohort will be for 48 weeks.

All participants who switched to the optional cohort will be considered as treatment failure to rifamycin-containing regimen.

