### 9.4.1. General Considerations

All efficacy and safety data will be summarized by treatment groups (Groups A and B). For the Group B, data from optional cohort will be analyzed separately.

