### 1.1. Objectives and Endpoints

Objectives	Endpoints
Primary	

 
Microbiological assessment in MGIT: To evaluate the efficacy of BDQ compared with rifamycin when administered as part of a treatment regimen with CAM and EB in adult participants with treatment-refractory MAC-LD at Week 24.
 
	
 
Percentage of participants with sputum culture conversion (defined as 3 consecutive negative sputum cultures taken at least 25 days apart) in MGIT at Week 24.
 

Secondary	

 
Microbiological assessment in 7H10 or 7H11 agar media: To evaluate the efficacy of BDQ compared with rifamycin when administered as part of a treatment regimen with CAM and EB in adult participants with treatment-refractory MAC-LD at Week 24.
 
	
 
Percentage of participants with sputum culture conversion (defined as 3 consecutive negative sputum cultures taken at least 25 days apart) in 7H10 or 7H11 agar media at Week 24.
 

 
Clinical assessment: To evaluate the efficacy of BDQ compared with rifamycin when administered as part of a treatment regimen with CAM and EB in adult participants with treatment-refractory MAC-LD at Week 24.
 
	
 
Change from baseline in patient-reported health status on total score of SGRQ at Week 24.
 

 
Microbiological assessment: To evaluate the efficacy of BDQ compared with rifamycin when administered as part of a treatment regimen with CAM and EB in adult participants with treatment-refractory MAC-LD up to Week 48.
 
	
 
Percentage of participants with sputum culture conversion (defined as 3 consecutive negative sputum cultures taken at least 25 days apart) in MGIT and 7H10 or 7H11 agar media at Week 48.
 
Percentage of participants with sputum culture negativity in MGIT and 7H10 or 7H11 agar media, respectively, at each visit after Week 2 per Schedule of Activities.
 
Time to sputum culture conversion (defined as 3 consecutive negative sputum cultures taken at least 25 days apart) in MGIT up to Week 48.
 
Time to positivity in MGIT up to Week 48.
 

Objectives	Endpoints

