## Analysis Phase

Analysis phase	Start date	End date
Screening	The date of signing the informed consent	1 day before the first study intervention intake
Investigation	Date of the first study intervention intake	If the participants are from Group A, Min [Week 48, study discontinuation]
		If the participants from Group B will not convert to the optional cohort, Min [Week 60, study discontinuation]
		If the participants will convert to the optional cohort, 1 day before the optional investigation phase
Optional investigation	Date of the first BDQ+CAM+EB intake for nonconverters came from Group B	For nonconverters came from Group B, Min [Optional Week 48, study discontinuation]
Follow-up	If the participants are in Group A and moved to follow-up period, end of the investigation phase + 1 day	Min [Week 60, study discontinuation]

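### SAP 5.4.2.2.1 names the wrong medium for the Week 24 agar test and does not say how optional-cohort switchers are classified on agar at Weeks 48 and 60

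*SAP*

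**What the plan says.** **Week 24.** SAP 1.1 lists, as the first secondary endpoint, the percentage with conversion ("defined as 3 consecutive negative sputum cultures taken at least 25 days apart) in 7H10 or 7H11 agar media at Week 24"). The method is in SAP 5.4.2.2.1, whose heading is agar. There a Cochran-Mantel-Haenszel (CMH) test stratified by region "will be used to compare sputum culture conversion rate in MGIT at Week 24". The following sentence promises the proportions and a treatment difference with a 95% CI, and names no medium.

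**Weeks 48 and 60.** The same section continues: "The proportion of participants who achieved sputum culture conversion of each treatment group (ie, as randomized) will be calculated with 95% CI". No test is planned. The only failure rule is: "Participants requiring a treatment regimen change to individualized regimen will also be considered as nonconverters".

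**Optional cohort elsewhere.** Protocol 4.1 states: "All participants who switched to the optional cohort will be considered as treatment failure to rifamycin-containing regimen". Protocol 9.4.1 adds: "For the Group B, data from optional cohort will be analyzed separately". For the neighbouring negativity endpoint, SAP 5.4.2.2.3 names both routes out of the assigned regimen: "If the subjects switch to individualized treatment regimen or to optional cohort, sputum culture should be considered as not negative".

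**The concern.** There are two drafting defects in one short section.

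First, the operative test sentence for an agar endpoint names MGIT. A programmer who follows it would run the primary comparison a second time and produce no agar test at Week 24.

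Second, the Week 48/60 rule combines grouping by randomized arm with a failure rule that mentions only the individualized regimen. Group B non-converters may start BDQ after Week 24, and nothing in this section says how they are classified at Weeks 48 and 60. If a program carried their later agar cultures forward under the randomized label, conversions reached on BDQ would appear in the rifamycin column. The descriptive difference between arms on agar would then shrink or vanish for a reason unrelated to rifamycin.

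**Working it through.** **1. Which medium is tested at Week 24**

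| SAP section | Subject | Between-group test at Week 24 |
|---|---|---|
| 5.3.2.1 | MGIT conversion (primary) | CMH by region |
| 5.4.2.2.1 | Heading: agar conversion | CMH by region, but of the MGIT rate |
| 5.4.2.2.2 | MGIT conversion | Summary only at Week 24 |
| 5.4.2.2.3 | Culture negativity | CMH by region for MGIT, plus a generalized linear model |

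No row tests agar conversion. The definition that 5.4.2.2.1 cites (SAP 5.3.1) is written for the MGIT endpoint, so the cross-reference does not supply the medium. The sentence looks like a carry-over from the primary analysis.

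**2. Whether the Week 48/60 rule already covers optional-cohort switchers**

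- Protocol 6.8.1 presents the individualized regimen as something additional to the optional cohort, and Protocol 6.8.2 forbids moving from the former to the latter. SAP 5.2 counts them as separate disposition categories. The term used in 5.4.2.2.1 therefore does not clearly include the optional cohort.
- Protocol 9.4.4 does fold optional-cohort switching into regimen change, but only for the regimen-change endpoint, and it says so explicitly.
- Where the SAP handles these switchers, it names them: in 5.4.2.2.3, and in the Week 48 censoring rule for time to conversion (5.4.2.1). Section 5.4.2.2.1 does not.
- SAP Appendix 2 declares no departure from the protocol on this point.

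The result is an omission, not a contrary rule.

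**3. The plan's own figure**

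Inputs from Protocol 9.2: 10% in Group B, a 20-point difference (so 30% in Group A), two-sided 5%, about 80% power, 62 per group. With pooled variance and no continuity correction:

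n = [1.960 × √(2 × 0.20 × 0.80) + 0.842 × √(0.10 × 0.90 + 0.30 × 0.70)]² / 0.20² = 61.6, rounded up to 62 per group. Power at 62 per group is 80.3%.

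The stated size is reproduced. It concerns MGIT at Week 24, and nothing in this point changes it. The documents give no figure for the agar analyses.

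**4. How far the two readings could differ (illustration)**

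Take 62 participants in Group B, of whom 10% convert on rifamycin: 6.2 converters and 55.8 non-converters. Let s be the share of non-converters who switch and q the share of switchers who convert on BDQ. Neither is given in the documents.

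- Switchers are non-converters: Group B = 6.2/62 = 10%.
- Switchers' conversions are counted: Group B = (6.2 + 55.8 × s × q)/62 = 0.10 + 0.90 × s × q.

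| s | q = 20% | q = 30% |
|---|---|---|
| 50% | 19.0% | 23.5% |
| 70% | 22.6% | 28.9% |
| 85% | 25.3% | 33.0% |

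**5. Time on BDQ**

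Under Protocol 6.8.2 the switch follows the Week 24 assessment, is decided by Week 32, and needs a 2-week washout. BDQ therefore starts at about Week 26 to 34. Exposure is 48 − 34 = 14 to 48 − 26 = 22 weeks by Week 48, and 26 to 34 weeks by Week 60. The schedule footnotes allow a later decision, which shortens both. Three negatives at least 25 days apart span at least 2 × 25 = 50 days. A conversion rate based on about 24 weeks of BDQ is thus too high for Week 48 and more plausible for Week 60.

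**The case against.** **The medium is obvious from context.** The heading and the endpoint list identify agar, MGIT has its own sections, and the estimate-and-CI sentence names no medium, so under that heading it can be read as agar. Protocol 9.4.4 says only that agar percentages are calculated, and the between-group test it names for conversion is at Week 60. So the slip breaks no explicit protocol test, and a reader who concludes that agar will never be compared goes too far. This stands as a limit on consequence. It does not make the test sentence correct: it still names MGIT, and no other SAP section supplies the agar test.

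**Switchers are already dealt with.** A reader might infer that the SAP credits BDQ conversions in the optional cohort to Group B. The documents do not support that. Protocol 4.1 and 4.2 make all such switchers treatment failures, and Protocol 9.4.1 separates their data. The SAP closes a switcher's investigation phase before optional dosing ("If the participants will convert to the optional cohort, 1 day before the optional investigation phase") and re-bases later visits to the optional start date (5.1.1, Table 3). Reporting as randomized fixes the group and denominator; it does not cancel a failure rule. All of this stands. What remains is that neither the phase boundary nor the visit windows say how a switcher is classified on agar at Week 48 or 60, and the missing-culture table in SAP 5.3.2.1 covers Week 24 only.

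**The magnitude is hypothetical.** This is correct. The 10% is a Week 24 MGIT planning value applied to agar at later visits, and s and q are assumptions.

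**Conclusion.** The point holds as a wording error and an omission. The Week 24 test sentence in SAP 5.4.2.2.1 is wrong as written, and that finding needs no assumption. The Week 48/60 rule is incomplete: it permits a reading contrary to Protocol 4.1, 4.2 and 9.4.1 but does not direct it.

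The consequence is limited. The SAP defines no key confirmatory secondary endpoints (5.4.1), and agar at Weeks 48 and 60 is descriptive. Optional-cohort switching opens only after the Week 24 assessment, so it cannot touch the primary analysis or agar at Week 24. If the silence were resolved the wrong way, Group B could read 19-33% instead of 10%, with less inflation at Week 48. That range depends wholly on the assumed 50-85% switching and 20-30% conversion. It shows why the rule should be stated and does not predict what the analysis will show.

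**What to change.** Make two edits in SAP 5.4.2.2.1:

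1. In the Week 24 test sentence, replace MGIT with 7H10 or 7H11 agar media.
2. For Weeks 48 and 60, state that a switch to an individualized regimen or to the optional cohort counts as non-conversion for the randomized group, and that optional-cohort agar results are summarised separately.

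The second edit follows the negativity rule in SAP 5.4.2.2.3 and restores what the protocol already says. The cost is two SAP sentences and a matching derivation in the agar datasets. Sample size, power, data collection and the primary analysis do not change.
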